3.3 FOLLOW-UP

Follow-up phone call to the patient to assess AEs will be performed on Day 3±1 (48 hours after the study drug dosing). Any SAE spontaneously reported by the patient within 30 days of dosing will be collected.

The study procedures schedule is summarized in Table 3.1.

Table 3.1 Schedule of visits and procedures

Test/Examination	Screening	Study treatments													ED ¹	Follow-up
		Time (Post-dose)														
Day	Day-4...Day 1	Day 1													Day 1	Day 3±1
		0.08	0.17	0.25	0.5	0.75	1	1.5	2	3	4	5	6	>1	48	
		5	10	15	30	45	60	90	120	180	240	300	360	>60		
Informed consent & screening n° assignment		X														
Demography		X														
Medical history and underlying disease		X														
Oral cavity examination		X														
Height		X														
Weight		X														
Vital signs		X														
Pregnancy test		X														
Extraction of a molar tooth	X (Day 1)															
Pain Intensity Assessment VAS (0-100 mm) ³	X	X														
Inclusion/exclusion criteria ⁴	X															
Randomization number assignment			X													
Patient's overall assessment (5-point scale) ⁵				X											X	X
Pain Relief Assessment VAS (0-100 mm)																
Time to first perceptible relief (TFPR) measured by stopwatch ⁶														X		
Time to meaningful pain relief (TMRP) measured by stopwatch ⁷														X		
Rescue medication (if applicable) ⁸															X ⁹	
Concomitant medications	X	X													X	X
Previous therapy(ies)	X	X														
Adverse events	X	X												X	X	

¹ Should the patient require rescue medication at any time during 6 hours post-dose, the last VAS measurement and patient's overall assessment will be performed before the rescue medication dosing. Subjects will be encouraged to postpone the rescue medication until after 1-hour post-dose. The ED assessments will be performed before rescue treatment; actual time of VAS will be captured.

² After surgery, before the study drug administration

³ Patients should mark actual time points of VAS measurement. Deviations from planned time points will not be considered as protocol deviations. Only omitted values will be considered as protocol deviations.

⁴ Confirmation of the Inclusion/Exclusion criteria prior to randomization

⁵ Patients should mark actual time points of VAS measurement. Deviations from planned time points will not be considered as protocol deviations. Only omitted values will be considered as protocol deviations.

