6. DETERMINATION OF SAMPLE SIZE¹

Sample size calculation was based on the paper of Seymour 1996 [3] concerning a randomized, double-blind, placebo-controlled study of treatment with placebo, paracetamol (500 and 1000 mg) and ketoprofen (12.5 and 25 mg).

The unadjusted AUC_{0-6h} values for placebo and ketoprofen were about 263 and 173 mmh⁻¹, respectively. The corresponding SD were 106 mm h⁻¹ (about 40% of the mean value for placebo AUC) and 121 mmh⁻¹ (about 70% of the mean value for ketoprofen 25 mg AUC).

The testing hypothesis for this trial is the superiority of ketoprofen versus placebo that in statistical term is:

H_0 : mean of placebo \geq mean of ketoprofen (no difference between treatments)

H_1 : mean of placebo $<$ mean of ketoprofen (clinically and statistically significant difference between the groups) $\Delta=90$ mm h⁻¹

A total of 58 subjects (29 subjects per group) will be necessary to assess a difference of 90 mm h⁻¹ between the groups with a power of 80%, $\alpha = 0.05$, SD=121 mmh⁻¹, and randomization rate of 1:1. Sample size calculation was performed using SAS 9.2².

Assuming a drop-out rate of 15%, 70 subjects in total (35 subjects per group) should be enrolled. Considering the screen-failure rate of about 30%, up to 100 patients will be screened in the study.

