7. REPLACEMENT OF THE MISSING DATA

7.1 PRIMARY EFFICACY

Considering that the primary variable AUC_{0-6h} is derived from pain intensity VAS measurements, analyses on primary and secondary variables without or with substitution of missing data, using the last observation carry forward (LOCF) methodology, has been considered in order to avoid bias in the inferential testing of treatment effect.

For LOCF analysis substitution of missing data will be applied only on all patients that have at least one VAS value post-baseline (patient compliant with ITT population definition). Missing post-baseline pain score will be replaced with previous one. **Baseline data (pre-dose) could be carried forward also.** Possibility to use baseline data comes from the data nature, which seems to be linearly decreasing over time. This will allow to calculate AUC in case of missing first post-baseline value (5 minutes).

If data be missing more than one time point after baseline, the data will be qualified as invalid. Consecutive missing values will be replaced with the last non-missing (observed) value. If more than two time points data are missing and after missing data some points have values (non-missing), then all missing sequence will be replaced with last non-missing value. In case of absence non-missing values after two missings, no replacement will be done and data will be find invalid for analysis. Possible cases are presented in table below:

¹ Cite from the Study Protocol

² SAS 9.2 <http://support.sas.com/documentation/92/>

Table 7.1 LOCF missing data replacement cases

Time points	Scale	Scale LOCF	AUC
0 (baseline)	A	A	Valid
1	B	B	
2	.	B	
3	.	B	
4	C	C	
5	D	D	
0 (baseline)	A	A	Valid
1	.	A	
2	B	B	
3	C	C	
4	D	D	
5	E	E	
0 (baseline)	A	A	Invalid
1	.	.	
2	.	.	
3	B	B	
4	C	C	
5	D	D	
0 (baseline)	A	A	Valid
1	B	B	
2	.	B	
3	.	B	
4	.	B	
5	C	C	
0 (baseline)	A	A	Invalid
1	B	B	
2	C	C	
3	.	.	
4	.	.	
5	.	.	

For the sensitivity analysis the fully conditional specification (FCS) regression method¹ will be used for replacing missing data.

SAS code example:

```
proc mi data=pain round=1. seed=139592 out=pain_imp;
  class trt;
```

¹ Van Buuren 2007; Brand 1999; Rubin 1987

http://documentation.sas.com/?docsetId=statug&docsetTarget=statug_mi_details07.htm&docsetVersion=14.3&locale=en

² Could be any other

```

fcs nbiter=20 reg (pain=time trt time*trt/details);
var pain time trt;
run;

```

Pain dataset description:

Alphabetic List of Variables and Attributes						

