8.1 INTENT-TO-TREAT POPULATION

The Intent-to-treat (ITT) population will include all randomized patients who receive at

least one dose of study medication and have at least one post-baseline¹ efficacy measurement; it will be based on the treatment randomized, regardless of the treatment actually received. The ITT will be used for all efficacy analyses. Subject will be summarized according to the treatment to which they were randomized.

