10.2 SECONDARY EFFICACY

Secondary efficacy variables will be analyzed only for ITT population.

¹ Clinically significant

AUC_{0-6h} without or with LOCF of pain relief profile between time 0 (baseline value of VAS) and 6 hours post-treatment. AUC_{0-6h} analysis will be based on **actual rather than scheduled timings** and will be calculated using the trapezoidal rule (see as per primary variable).

Pain profile – Pain intensity profile will be analyzed using Analysis of Variance (ANOVA) for repeated measurements. The model will include fixed effect terms for clinical site, time point and treatment. Time point will be specified as a repeated measurement. In order to select an appropriate matrix for the observations within each subject, 3 models will be fitted using the compound symmetry, Huynh-Feldt and unstructured structures. The matrix for the final model will be selected using Akaike's Information Criterion where the lowest value indicates the best fit. The importance of the treatment-by-site interaction will be investigated but if the term is not significant at the 10% level, it will be excluded from the final model. The adjusted least squares mean will be estimated for each combination of time point and treatment. The estimated treatment difference between OKITASK® and placebo at each time point will be presented together with the corresponding 95% confidence interval. Pain profile will be analyzed based on **scheduled rather than actual timings**.

SAS code example:

```
proc mixed data=locf method=REML order=internal1;
  class patid site trt time;
  model pain = trt time trt*time
    site trt*site/ intercept ddfm=satterth;
  repeated time/ type=CS2 subject=patid(trt);
  lsmeans trt*time/ diff=all cl;
run;
```

Pain relief – Pain relief will be analyzed in the same way.

LOCF replaced data of pain intensity and pain relief will be presented graphically by treatments and time points.

Time to first perceptible relief (TFPR)³ – Kaplan-Meier curve and Log rank test will be used to describe and test treatment profile differences. In table it will be presented with median, 95% CI and p-value from Log rank test.

Time to meaningful pain relief (TMPR)⁴ – Kaplan-Meier curve and Log rank test will be used to describe and test treatment profile differences. In table it will be presented with median, 95% CI and p-value from Log rank test.

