12. TABLE EXAMPLES¹

Table 12.1 Disposition

	OKITASK® N = XX	PLACEBO N = XX
Screened		xx
Safety population	xx (xx.x%)	xx (xx.x%)
Intent-to-treat (ITT) population	xx (xx.x%)	xx (xx.x%)
Per-Protocol (PP) population	xx (xx.x%)	xx (xx.x%)
Study completion	xx (xx.x%)	xx (xx.x%)
Early termination	xx (xx.x%)	xx (xx.x%)
Adverse event	xx (xx.x%)	xx (xx.x%)
Death	xx (xx.x%)	xx (xx.x%)
Patient required rescue medication	xx (xx.x%)	xx (xx.x%)
Lost to follow-up	xx (xx.x%)	xx (xx.x%)
Consent withdrawn	xx (xx.x%)	xx (xx.x%)
Investigator decision	xx (xx.x%)	xx (xx.x%)
Protocol violation, including non-compliance	xx (xx.x%)	xx (xx.x%)
Patient required prohibited medications		
Protocol entry criteria not met	xx (xx.x%)	xx (xx.x%)
The patient starts of another study drug	xx (xx.x%)	xx (xx.x%)
Study is stopped by Sponsor decision	xx (xx.x%)	xx (xx.x%)
Study is stopped by regulatory instance / ethics committee	xx (xx.x%)	xx (xx.x%)
Pregnancy	xx (xx.x%)	xx (xx.x%)
Other	xx (xx.x%)	xx (xx.x%)

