12.2 EFFICACY

12.2.1 Primary efficacy

Table 12.9 Primary efficacy. Visual Analogue Scale. Pain Intensity Assessment with LOCF. ITT population. N = XX

Parameter Treatment	Result				
	N	Mean (SD)	Median	Min	Max
Visual Analogue Scale. Pain Intensity. AUC_{0-6h}. LOCF					
OKITASK [®]	XX	xx.x (xx.x)	xx.x	xx.x	xx.x
PLACEBO	XX	xx.x (xx.x)	xx.x	xx.x	xx.x
p-value ANOVA = 0.***					
Visual Analogue Scale. Pain Intensity. AUC_{0-6h}. Multiple Imputation					
OKITASK [®]	XX	xx.x (xx.x)	xx.x	xx.x	xx.x
PLACEBO	XX	xx.x (xx.x)	xx.x	xx.x	xx.x
p-value ANOVA = 0.***					

Table 12.10 Primary efficacy. Visual Analogue Scale. Pain Intensity Assessment without LOCF. PP population. N = XX

Parameter Treatment	Result				
	N	Mean (SD)	Median	Min	Max
Visual Analogue Scale. Pain Intensity. AUC_{0-6h}					
OKITASK [®]	XX	xx.x (xx.x)	xx.x	xx.x	xx.x
PLACEBO	XX	xx.x (xx.x)	xx.x	xx.x	xx.x
p-value ANOVA = 0.***					

Table 12.11 Primary efficacy. Visual Analogue Scale. Pain Intensity Assessment with LOCF. ITT population. N = XX

Parameter Treatment	Result				
	N	Mean (SD)	Median	Min	Max
Visual Analogue Scale. Pain Intensity. AUC_{0-6h}. LOCF					
OKITASK [®]	XX	xx.x (xx.x)	xx.x	xx.x	xx.x
PLACEBO	XX	xx.x (xx.x)	xx.x	xx.x	xx.x
p-value ANOVA = 0.***					
Visual Analogue Scale. Pain Intensity. AUC_{0-6h}. Multiple Imputation					
OKITASK [®]	XX	xx.x (xx.x)	xx.x	xx.x	xx.x
PLACEBO	XX	xx.x (xx.x)	xx.x	xx.x	xx.x

¹ Clinically significant² Parameters with normal values or NCS (not clinically significant) in both groups should be omitted from this table

Parameter Treatment	Result				
	N	Mean (SD)	Median	Min	Max
p-value ANOVA = 0.***					

Table 12.12 Primary efficacy. Visual Analogue Scale. Pain Intensity Assessment without LOCF. PP population. N = XX

Parameter Treatment	Result				
	N	Mean (SD)	Median	Min	Max
Visual Analogue Scale. Pain Intensity. AUC_{0-6h}					
OKITASK [®]	XX	XX.X (XX.X)	XX.X	XX.X	XX.X
PLACEBO	XX	XX.X (XX.X)	XX.X	XX.X	XX.X
p-value ANOVA = 0.***					

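### The FCS sensitivity imputation ignores the patient's own pain readings, so its test of AUC0-6h is anti-conservative when values after a patient leaves are filled

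*SAP*

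**What the plan says.** SAP section 7.1 names fully conditional specification regression as the sensitivity method for missing VAS scores and gives one code example. The imputation statement is "fcs nbiter=20 reg (pain=time trt time*trt/details" and the variable list is "var pain time trt". The dataset description below it has a single pain column, with patient ID, time, treatment and site as separate columns. That is one row per reading. Patient ID and site are not used.

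Section 10.1 gives this analysis the task of confirming the LOCF result. Its test is an ANOVA on one AUC0-6h per patient.

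On who is analysed, section 8.1 requires only one post-baseline measurement for ITT and adds "The ITT will be used for all efficacy analyses". Table 12.9, an ITT table, has a block headed "Visual Analogue Scale. Pain Intensity. AUC_{0-6h}. Multiple Imputation".

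Partial profiles are foreseen. The last VAS is taken before rescue (section 3.2), and Table 12.1 lists "Patient required rescue medication" as a reason for early termination. On timing, the first footnote of Table 3.1 says "Subjects will be encouraged to postpone the rescue medication until after 1-hour post-dose".

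The repeated-measures model in section 10.2 does treat readings as correlated within a patient: "repeated time/ type=CS2 subject=patid(trt" (the 2 after CS is a footnote mark).

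**The concern.** An imputed score should reflect what is known about that patient. Here a patient with scores of 80 mm and one with scores of 20 mm in the same arm receive draws from the same distribution at the same time point. Two things follow.

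- **Variance.** The error term of the ANOVA is the between-patient variance of AUC. Independent draws average out inside an AUC, so filled patients have AUCs that are too alike. The model also fits repeated readings as if they were independent, so its parameters look more precise than they are and the between-imputation variance is too small.
- **Bias.** If patients leave because of pain, their later scores are pulled back to the arm's line. The estimated difference shrinks if this happens more often on placebo.

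At stake is the value of the confirmation. A test with too small a standard error can appear to support the LOCF result when it should not.

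**Working it through.** **Inputs from the SAP.** 35 patients per arm; baseline plus 12 scheduled times; AUC means 263 and 173, difference 90, SD 121 mm h (section 6); two-sided F-test at 0.05, with superiority declared only if the OKITASK mean is lower (section 10.1). For loss: "Assuming a drop-out rate of 15%, 70 subjects in total (35 subjects per group) should be enrolled".

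**The plan's own figure.** n per arm = 2 × (1.960 + 0.842)² × 121² / 90² = 28.4, so 29 per arm and 58 in total, as stated. 58 / 0.85 = 68.2, so 69, or 70 with equal arms. The SAP gives no operating figure for the FCS analysis.

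**Schedule arithmetic.** Take a patient last measured at 60 min. The trapezoid weights at 90, 120, 180, 240, 300 and 360 min are 0.5, 0.75, 1, 1, 1 and 0.5 h.

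- Sum = 4.75 h. Sum of squares = 4.0625, root 2.02 h.
- With a common score SD σ, independent draws give this part of the AUC an SD of 2.02σ.
- With within-patient correlation ρ, the real SD is σ√(ρ × 4.75² + (1 − ρ) × 4.0625). This is 4.34σ at ρ = 0.8 and 3.65σ at ρ = 0.5.
- Ratios: 2.02 / 4.34 = 46% and 2.02 / 3.65 = 55%.

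**Simulation 1, no treatment effect.** Assumed, because the SAP does not give them:

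- linear mean profile from 55 mm, unbounded normal scores;
- compound symmetry of 0.5 or 0.8, or a random intercept plus decaying correlation;
- 25 imputations, Rubin pooling with small-sample degrees of freedom;
- trailing values filled, with 15% of patients having trailing loss.

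There were 8,000 trials per scenario (Monte Carlo SE about 0.25 to 0.3 points).

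| Timing of loss | Two-sided type I error, SAP model | False superiority (nominal 2.5%) |
|---|---|---|
| After 1 h, random | 5.9–6.8% | 3.0–3.5% |
| Any time, random | 6.8–7.2% | 3.3–3.6% |
| Within first hour, random | 7.8–8.3% | 3.9–4.1% |
| After 1 h, pain-driven | 6.1–7.0% | 3.0–3.6% |

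Regressing each time point on treatment, baseline and the two previous readings gave 4.2–5.2% (1.9–2.8%) in the same trials. The pooled SE was 5–11% below the true SD of the estimate under the SAP model, against −1% to +2% under patient-level imputation. With less loss, the SAP model gave 5.9–6.8% at 10% of patients and 5.1–6.0% at 5%. With isolated gaps only (2% of readings), it gave 4.3–5.1%, against 4.1–5.1% for patient-level imputation.

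**Simulation 2, written separately.** Patient SD 19.5 and residual SD 10 mm (AUC SD about 119), random trailing loss starting at 90–240 min, SAP model:

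| Patients with trailing loss | AUC SD after filling | Mean SE / true SE | Type I error |
|---|---|---|---|
| 15% | 112 | 27.0 / 29.4 | 7.0% |
| 30% | 104 | 25.7 / 30.6 | 9.5% |
| 50% | 94 | 24.1 / 32.8 | 14.6% |

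Imputation from the patient's own readings gave 4.6–5.3% and an AUC SD of about 119 throughout. The 30% and 50% rows have no source in the SAP and only show the trend. One isolated missing value in 15–50% of patients gave 5.2–5.9%, against 4.5–5.6% on the complete data.

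**Bias (simulation 1).** With a true difference of 90 and pain-driven loss of about 15% on placebo and 8–9% on active, the mean estimate was about 83 to 85 under the SAP model. It was 88 to 90 with patient-level imputation and 89 to 90 on full data. Under random loss neither method was biased.

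**The case against.** **The harm needs trailing gaps to be filled.** Section 7.1 declares long trailing gaps invalid, and section 10.1 says the FCS test confirms the LOCF analysis, which could mean the same patients. PROC MI also fills only rows that exist, and the SAP does not say whether rows exist after a patient leaves. This stands as a condition on the size. If only isolated gaps are filled, the error rate is close to nominal. But the invalidity rule sits in the LOCF text, no such limit is stated for FCS, and section 8.1 and Table 12.9 point to the whole ITT population.

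**The effect is small and the inputs are assumed.** The 15% is a sample-size allowance, not a rate of partial profiles, and at 5% loss the test is near nominal. The SAP states neither a pooling rule nor a number of imputations. All of this is true, and is why ranges are shown.

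**The simulated scores are unbounded.** A line from 55 mm with AUC 173 ends at 2 × 173 / 6 − 55 = 2.7 mm, so many simulated active scores at 6 h are negative. Clipping scores to 0–100 cuts the full-data difference to about 76 to 79. Only the direction of the bias should therefore be relied on. The type I inflation persists after clipping: 5.6–6.3% at 15% random loss after 1 h.

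**It is a supportive test and the code is an example.** The first part is correct and limits the consequence. On the second, the SAP describes no other imputation model.

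**Conclusion.** The concern holds. The model omits everything known about the individual patient, which can be read from the code and needs no assumption. If trailing values are filled for about 15% of patients, two-sided type I error is roughly 6 to 8% instead of 5%, and false superiority 3 to 4% instead of 2.5%. These figures rest on assumed correlation, timing and share of loss, Rubin pooling and 25 imputations. The inflation grows with the share of partial profiles and nearly vanishes at 5% loss or with isolated gaps. Pain-driven loss that is heavier on placebo also biases the estimate towards no difference.

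The consequence stays within the sensitivity test. The LOCF and per-protocol tests are unaffected, and requiring a second test to agree cannot raise the false-positive rate of the primary one. The plan should be corrected before analysis, because as written this test cannot be relied on to confirm the LOCF result.

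**What to change.** Replace the example in section 7.1 as follows:

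1. Transpose to one row per patient with one column per scheduled time.
2. Impute each time point, by FCS or by monotone regression where the gap is trailing, from treatment, baseline VAS and the patient's preceding readings. Using the last two keeps the model estimable with about 70 patients, and this is the version tested above. For gaps with later readings, FCS may use those too.
3. State whether ITT patients with trailing gaps are included (sections 8.1 and 12.2.1 imply that they are) and how scores after rescue are treated in the analysis. The latter is a separate decision that the imputation should not settle by default.
4. Compute AUC0-6h per patient in each completed dataset, using the scheduled time for imputed values in line with section 10.1. Fit the primary ANOVA in each and pool by Rubin's rules with a stated number of imputations.
5. Report the pooled difference, confidence interval and p-value in the multiple-imputation block of Table 12.9.

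The cost is a few lines of SAS and of SAP text, with no new data.

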7.2 ADVERSE EVENTS

Treatment emergency sign and symptom (TESS) will be AEs which started after the first study drug dose. Following rules will be applied (Table 7.2):

Table 7.2 TESS classification algorithm

AE start date			Algorithm
Day	Month	Year	
Missed	Missed	Present	If year \geq year of the first drug dose – TESS
Missed	Missed	Missed	The worst case – TESS
Missed	Present	Missed	The worst case – TESS
Present	Missed	Present	If year \geq year of the first drug dose – TESS
Missed	Present	Present	If month and year \geq date of the first study drug dose (month and year) – TESS
Present	Missed	Missed	The worst case – TESS
Present	Present	Missed	The worst case – TESS
Present	Present	Present	Compare dates of AE and the first study drug dose. In case of dates equality qualification will be performed by the sponsor and investigator (questionable TESS)

All questionable TESS flags will be exported to the MS Excel file and send to the sponsor for resolution.

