3.1 SCREENING

At Screening after signing the informed consent form, patient's demography, medical history and concomitant medications will be collected, oral cavity will be examined, weight and vital signs will be measured and pregnancy test will be performed for inclusion/exclusion criteria assessment. Screening procedures might take up to 4 days before the scheduled tooth extraction procedure including the actual day of extraction.

On Day 1 the patient will undergo extraction of a molar tooth as indicated for the patient's dental condition. The tooth extraction will be conducted using routine technics and anesthetics (recommended types of anesthesia are provided in section 5.9 Concomitant and rescue therapy of the protocol). After that the patient will stay at the site for treatment of pain syndrome according to the protocol.

Pain intensity will be assessed using VAS within 3 hours after the tooth extraction procedure. Patient's overall assessment will be also recorded. If pain intensity on VAS is above 30 mm and pain relief is required, the patient will be randomized in the study.

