10.3.2 Adverse events and serious adverse events assessment

All adverse events will be coded with MedDRA dictionary (last available version at the moment of coding).

Before the start of statistical analysis all AEs will be qualified as TESS (AEs started after the first study drug dose or worsening conditions for previously available AEs) and not TESS. In case of missing dates in AE reporting dates will be replaced as described in section 7.

Adverse events of the study time (TESS) will be presented by frequencies (number of patients with AEs and number of events) grouped by treatment, System Organ Class (SOC) and Preferred terms (PT) and relation to the study drug and severity.

All AEs (TESS and not TESS) will be presented in listings.

Serious adverse events will be presented separated from all AEs with tables and listings.

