12.3 SAFETY PARAMETERS

**Table 12.20 Concomitant medication. During the study time.
Safety population. N = XX**

ATC Group Drug (ATC code)	OKITASK® N = XX	PLACEBO N = XX
ATC Group (level 3)	xx (xx.x%)	xx (xx.x%)
Drug 1 (ATC level 5)	xx (xx.x%)	xx (xx.x%)
Drug 2 (ATC level 5)	xx (xx.x%)	xx (xx.x%)
...		

Table 12.21 Adverse events. Summary table. Safety population. N = XX

Parameter	OKITASK® N = XX x (%)	PLACEBO N = XX x (%)	
		Y	Y
Patients with AE/SAE	xx (xx.x%)	xx	xx (xx.x%)
Patients with SAE	xx (xx.x%)	xx	xx (xx.x%)
Patients with death outcome AE/SAE	xx (xx.x%)	xx	xx (xx.x%)
Patients with mild and moderate AE/SAE	xx (xx.x%)	xx	xx (xx.x%)
Patients with severe AE/SAE	xx (xx.x%)	xx	xx (xx.x%)
Patients with related or possibly related AE/SAE	xx (xx.x%)	xx	xx (xx.x%)
Patients with related or possibly related severe AE/SAE	xx (xx.x%)	xx	xx (xx.x%)

¹ If data allow² if any

Parameter	OKITASK® N = XX		PLACEBO N = XX	
	x (%)	Y	x (%)	Y
Patients with AE/SAE leaded to discontinuation	xx (xx.x%)	xx	xx (xx.x%)	xx

X = patients with at least one event in the group
 % = percent of patients with at least one event in the group
 Y = total number of events

Table 12.22 Adverse events started before taking the first drug dose. Safety population. N = XX

MEDDRA System Organ Class term MEDDRA Preferred term	OKITASK®		PLACEBO	
	x (%)	Y	x (%)	Y
Patients with AEs/SAEs	xx (xx.x%)		xx (xx.x%)	
SOC term	xx (xx.x%)	xx	xx (xx.x%)	xx
Preferred term 1	xx (xx.x%)	xx	xx (xx.x%)	xx
Preferred term 2	xx (xx.x%)	xx	xx (xx.x%)	xx
...				

X = patients with at least one event in the group
 % = percent of patients with at least one event in the group
 Y = total number of events

Table 12.23 Adverse events. Safety population. N = XX

MEDDRA System Organ Class term MEDDRA Preferred term	OKITASK®		PLACEBO	
	x (%)	Y	x (%)	Y
Patients with AEs/SAEs	xx (xx.x%)		xx (xx.x%)	
SOC term	xx (xx.x%)	xx	xx (xx.x%)	xx
Preferred term 1	xx (xx.x%)	xx	xx (xx.x%)	xx
Preferred term 2	xx (xx.x%)	xx	xx (xx.x%)	xx
...				

X = patients with at least one event in the group
 % = percent of patients with at least one event in the group
 Y = total number of events

Table 12.24 Adverse events and relation to the study drug. Safety population. N = XX

MEDDRA System Organ Class term MEDDRA Preferred term	Relation	OKITASK®		PLACEBO	
		x (%)	Y	x (%)	Y
Patients with AE/SAE		xx (xx.x%)		xx (xx.x%)	
	Highly probable	xx (xx.x%)		xx (xx.x%)	
	Probable	xx (xx.x%)		xx (xx.x%)	
	Possibly	xx (xx.x%)		xx (xx.x%)	

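### Treatment-emergent AEs are defined two ways: section 7.2 and Table 7.2 use start date only, section 10.3.2 also counts worsening, and same-day events have no deciding criterion

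*SAP*

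**What the plan says.** Section 7.2 opens with a definition: "Treatment emergency sign and symptom (TESS) will be AEs which started after the first study drug dose". Table 7.2 then turns it into rules, one row for each pattern of present or missing day, month and year of the AE start date. For a complete date the rule is "Compare dates of AE and the first study drug dose", followed by "In case of dates equality qualification will be performed by the sponsor and investigator (questionable TESS"). Below the table the SAP adds: "All questionable TESS flags will be exported to the MS Excel file and send to the sponsor for resolution".

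Section 10.3.2 requires every AE to be qualified as TESS or not TESS before the statistical analysis starts, and there TESS means "AEs started after the first study drug dose or worsening conditions for previously available AEs". It refers back to section 7 only for incomplete dates: "In case of missing dates in AE reporting dates will be replaced as described in section 7". The TESS flag decides which events enter the main AE frequency tables.

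Among the output shells in section 12.3, Table 12.22 is titled "Adverse events started before taking the first drug dose. Safety population", so it is defined by onset. Listing 12.1 shows one start date and one severity per AE record.

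On timing, section 3.1 states: "On Day 1 the patient will undergo extraction of a molar tooth". The pain score that qualifies a patient for randomization is taken within 3 hours of the extraction, and the baseline footnote to section 8.1 puts time 0 on Day 1 as well. Screening may take up to 4 days including the extraction day, and Table 3.1 has AEs collected from screening on.

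**The concern.** An AE that is present before the dose and gets worse after it is treatment-emergent under section 10.3.2 and not treatment-emergent under section 7.2. The only classification rules in the SAP follow the narrower definition, and nothing says which section prevails. Two programmers working from the same document could produce different TESS tables.

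The rate of adverse events is one of the secondary objectives in section 5.2, and the TESS frequencies are the main output for it. The design makes pre-dose events plausible: every patient has an extraction shortly before a single dose. Whether worsening of such events after dosing counts should be fixed by rule, not left to whoever resolves the flags.

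**Working it through.** No figure in the SAP depends on this point, so the check sets the definitions and rules side by side.

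**Step 1. Where the definitions differ.**

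| AE | Section 7.2 | Section 10.3.2 |
|---|---|---|
| Starts after the dose | TESS | TESS |
| Starts before the dose, does not worsen | not TESS | not TESS |
| Starts before the dose, worsens after it | not TESS | TESS |

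They disagree only on the last line.

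**Step 2. What Table 7.2 uses.** Three date parts, each present or missing, give 2 x 2 x 2 = 8 rows:
- Year missing (4 rows): TESS as the worst case.
- Month missing, year present (2 rows): TESS if the year is not before the dose year.
- Only the day missing (1 row): TESS if month and year are not before those of the dose.
- Complete date (1 row): compare with the dose date; if equal, questionable.

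The rows state when an event is TESS; not TESS for an earlier date is the implied complement. No row takes a worsening date, a change in severity or a clock time.

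**Step 3. Apply the rows to an AE that starts before the dose and worsens after it.** Section 10.3.2 calls it TESS in every case.

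| Onset | Complete date (1 row) | Incomplete date (7 rows) |
|---|---|---|
| Day 1, after extraction, before dosing | questionable | TESS in all 7 |
| Before Day 1, same month as the dose | not TESS | TESS in all 7 |
| Before Day 1, earlier month, same year | not TESS | not TESS in 1 (only the day missing), TESS in 6 |
| Before Day 1, earlier year | not TESS | not TESS in 3 (only the day missing; month missing with year present), TESS in 4 |

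Extraction and dosing both fall on Day 1, so a post-extraction, pre-dose AE carries the dose date. None of the 8 rows makes it automatically not TESS. The direct conflict with section 10.3.2 lies in the onsets before Day 1. There, the same worsened event is excluded when its date is fully known, yet included when, for example, the year is missing.

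**Step 4. The questionable events.** Section 7.2 gives no criterion for resolving them. Suppose the reviewers know that onset preceded the dose and that the event then worsened. Under section 7.2 the answer is not TESS; under section 10.3.2 it is TESS. A recorded onset time would not settle it, because the order of onset and dose is not in dispute; the definition is.

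**Step 5. Size.** With 35 planned patients per arm, one patient moved into or out of the TESS count, and having no other TESS, changes that arm's rate by 1/35 = 0.0286, or 2.9 percentage points. The SAP contains no AE rate from which to say how many patients are affected.

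**The case against.** The best defence is that section 10.3.2 governs. It is the AE analysis section, it names worsening, and it sends the reader to section 7, which is headed as dealing with missing data, only for missing dates. On that reading Table 7.2 is a date-handling aid. This stands in part: the two sections can be reconciled that way, and the authors may have meant it. But the first sentence of section 7.2 is worded as a definition, the last row of the table classifies complete dates too, and no sentence gives section 10.3.2 precedence.

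A second defence is that the shells in section 12 are only examples, and that a worsening may be entered as a separate AE record with its own start date. How worsening is recorded is commonly left to the protocol or the eCRF instructions, which are not shown, so its absence here is no fault. Even then, a worsening on Day 1 would carry the dose date and again be flagged as questionable.

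Third, nothing vanishes from reporting. Pre-dose events are tabulated in Table 12.22 and all AEs are listed. That is right; what is at issue is the TESS frequencies.

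A reader might also infer that events of the extraction that begin before dosing and worsen on drug are all classed as not treatment-emergent. The equal-dates row rules that out: with a complete date they are questionable, and with an incomplete date they are TESS. The reviewers are not confined to the start date and may well apply section 10.3.2.

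**Conclusion.** The inconsistency is real. Section 7.2 and Table 7.2 classify on start date only, and section 10.3.2 also counts worsening. Applied as written, Table 7.2 excludes events that section 10.3.2 calls TESS when they have a complete start date before Day 1, or a partial date that places them in an earlier month or year. This rests on reading an earlier date as not TESS, which the table implies without saying so. For Day 1 pre-dose events the outcome is undetermined rather than wrong.

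The effect is 2.9 percentage points per reclassified patient in an arm, assuming 35 dosed patients per arm. A reader might go further and multiply assumed rates of post-extraction AEs and of worsening to get a number of patients lost from the tables. The SAP supports neither rate, and those events are not the ones excluded automatically, so no such total should be given.

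**What to change.** - Use the section 10.3.2 definition in section 7.2, so that there is one definition.
- Add a branch to Table 7.2: an AE that started before the dose and increased in severity or became serious after it is TESS, dated at the worsening.
- Apply the same criterion to the questionable same-day events, with the resolution done blinded and before database lock.
- State that worsened events count in Tables 12.21 and 12.23 to 12.30, while the original pre-dose event stays in Table 12.22.

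The cost is SAP wording and one branch in the algorithm. The downside is a slightly higher TESS count in both arms.
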